Appendix C: Guidelines for Women of Childbearing Potential and Fertile Male Patients Women

Women of childbearing potential (WOCBP), defined as all women capable of becoming pregnant, and men with partners who are WOCBP, must use highly effective contraception during the study and for 90 days following the last dose of study drug.

Men

All men must use highly effective contraception during the study and for 90 days after stopping treatment with all partners who are WOCBP (defined as all women physiologically capable of becoming pregnant).

Acceptable Contraception Methods:

Highly effective contraception is defined as either:

True Abstinence When this is in line with the preferred and usual lifestyle of the subject.

Periodic abstinence (e.g., calendar, ovulation, symptothermal, post-ovulation methods) and withdrawal are not acceptable methods of

contraception.

Sterilization When a WOCBP has had surgical bilateral oophorectomy (with or without

hysterectomy) or tubal ligation at least six weeks prior to study entry. In case of oophorectomy alone, only when the reproductive status of the woman has been confirmed by follow-up hormone level assessment.

Male Partner Sterilization When there is appropriate post-vasectomy documentation of the absence of sperm in the ejaculate.

Use of a combination of any two of the following (one from a + one from b) is acceptable:

- a) Placement of an intrauterine device (IUD) or intrauterine system (IUS) or established use of oral, injected or implanted hormonal methods of contraception.
- b) Barrier methods of contraception: condom or occlusive cap (diaphragm or cervical/vault caps) with spermicidal foam/gel/film/cream/vaginal suppository.

Fertile male subjects, defined as all males physiologically capable of conceiving offspring, with female partners of childbearing potential must use condoms plus spermicidal agent during the study treatment period and for 90 days after the last dose of the study drug, and should not father a child during this period.

Male subjects must also refrain from donating sperm during their participation in the study and for **90 days after the last dose of the study drug.**

Unacceptable Contraception Methods for WOCBP include:

- IUD progesterone T
- Female condom
- Natural family planning (rhythm method) or breast-feeding

CONFIDENTIAL

Study Drug: AC699 Sponsor/Development Innovations Study Numbers: AC699-001/BRE 401

- Fertility awareness
- Withdrawal
- Cervical shield

Pregnancies

To ensure subject safety, each pregnancy in a subject on study treatment must be reported to the Development Innovations Safety Department within 24 hours of learning of its occurrence. The pregnancy should be followed-up for 3 months after the termination of the pregnancy to determine outcome, including spontaneous or voluntary termination, details of the birth, and the presence or absence of any birth defects, congenital abnormalities, or maternal and/or newborn complications.

Pregnancy should be recorded on a Clinical Study Pregnancy Form and reported by the Investigator to the **Development Innovations Safety Department**. Pregnancy follow-up should be recorded on the same form and should include an assessment of the possible relationship to the study drug of any pregnancy outcome. Any SAE experienced during pregnancy must be reported on the SAE Report Form.

Pregnancy outcomes must be collected for the female partners of any males who took study treatment in this study. Consent to report information regarding these pregnancy outcomes should be obtained from the mother.

Final Protocol: 07 May 2024 Version 4.0

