3. STUDY PATIENT POPULATION AND DISCONTINUATION

3.1 Inclusion Criteria

Patients must meet all the following criteria in order to be included in the research study:

1. Written informed consent, according to local guidelines, signed and dated prior to the performance of any study-specific procedures, sampling, or analyses

CONFIDENTIAL

Study Drug: AC699 Sponsor/Development Innovations Study Numbers: AC699-001/BRE 401

- 2. Adult male and female patients, at least 18 years-of-age at the time of signature of the informed consent form (ICF)
- 3. Female participants must meet one of the following criteria described in a) or b):
 - a) Premenopausal or perimenopausal women must receive concurrent treatment with a luteinizing hormone-releasing hormone (LHRH) agonist beginning at least 4 weeks before the start of trial therapy and agree to continue the LHRH agonist throughout the duration of study treatment, have a negative serum pregnancy test within 7 days of initiating treatment, and agree to follow guidelines for use of highly effective contraception as outlined in Appendix C during the study and for 90 days following the last dose of study drug.
 - b) Postmenopausal women must be defined by as one of the following:
 - i. Age \geq 60, or
 - ii. Spontaneous amenorrhea (i.e., in the absence of chemotherapy, tamoxifen, toremifene, or ovarian suppression) for ≥12 months following cessation of all exogenous hormonal treatment, or
 - iii. 6 months of spontaneous amenorrhea with serum follicle-stimulating (FSH) levels and an estradiol value in the post-menopausal range per institutional standards), or
 - iv. Prior bilateral oophorectomy performed at least 6 weeks before screening, with or without hysterectomy
- 4. Eastern Cooperative Oncology Group (ECOG) Performance Status score of 0 or 1 (Appendix A)
- 5. Patients with a confirmed diagnosis of advanced, unresectable, and/or metastatic breast cancer following disease progression on standard treatment, or for whom no therapy of proven efficacy exists, or who are not amenable to standard therapies
- 6. Patient has a histologically and/or cytologically confirmed diagnosis of estrogen-receptor positive (ER+) breast cancer
- 7. Patient with HER2-negative breast cancer as defined by American Society of Clinical Oncologists/College of American Pathologists (ASCO/CAP) guidelines (Wolff et al. 2018)

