3.2 Exclusion Criteria

Patients who meet any of the following criteria will be excluded from study entry:

- 1. Treatment with any of the following:
- any cytotoxic chemotherapy, investigational agents or other anti-cancer drugs for the treatment of locally advanced or metastatic breast cancer within 14 days prior to the first administration of AC699
- >3 prior chemotherapy regimens for locally advanced or metastatic breast cancer
- radiation therapy within 14 days prior to first study drug administration that did not resolve to tolerable toxicity, or prior irradiation to >25% of bone marrow. Prior palliative radiotherapy to metastatic lesion(s) is permitted, provided it has been completed 7 days prior to study enrollment and no clinically significant toxicities are expected (e.g., mucositis, esophagitis).
- major surgery within 21 days prior to the first study drug administration (exception: patients may enroll if fully recovered or without intolerable or clinically significant adverse effects but at least 14 days must have elapsed between major surgery and first study drug administration)

CONFIDENTIAL

Sponsor/Development Innovations Study Numbers: AC699-001/BRE 401

Final Protocol: 07 May 2024 Version 4.0

- use of prophylactic growth factors and blood transfusions ≤14 days prior to the first study drug administration
- proton pump inhibitors should not be used within at least 48 hours prior to C1D1 and are prohibited during the study.
- 2. With the exception of alopecia and ≤ Grade 2 peripheral neuropathy, any unresolved toxicities from prior therapy greater than Common Terminology Criteria for Adverse Events (CTCAE) Grade 1 at the time of starting study treatment. Note: Subjects with chronic Grade 2 toxicities that are asymptomatic or adequately managed with stable medication may be eligible with approval by the Medical Monitor and/or Sponsor.
- 3. Known symptomatic brain metastases requiring the use of systemic corticosteroids ≥10 mg/day prednisone or equivalents. Asymptomatic and treated, or asymptomatic untreated brain metastases are allowed as long as patients are clinically stable. Stable doses of anticonvulsants are allowed.

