5.4.2 Prohibited Concomitant Medications

The following treatments are prohibited while in this study:

• No other investigational therapy should be given to patients. No anticancer agents other than the study treatments should be given to patients. If such agents are required for a patient, then the patient must first be withdrawn from the study.

CONFIDENTIAL

Sponsor/Development Innovations Study Numbers: AC699-001/BRE 401

Final Protocol: 07 May 2024 Version 4.0

- Anticoagulation with coumarin-derivatives is not permitted. However, the use of anticoagulants to keep the port line patent will be permitted. Should a thrombotic event occur while the patient is in the study and receives anticoagulant treatment, and the patient remains in the study, oral Xa inhibitors will be the preferred anticoagulant treatment.
- Proton pump inhibitors are prohibited due to their long PD effect. This type of drugs should be replaced with H2-antagonists or antacids.
- Any new or concomitant QT prolonging medications within the last 6 months.

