6.9 Other Safety Parameters

Additional safety parameters including hepatoxicity – liver assessment, and post-menopausal status will be listed only.

7 Other Analyses

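### Appendix C accepts hormonal contraception in the same women whom inclusion 3a puts on an LHRH agonist, and exclusion 1 and Section 5.4.2 make no exception for that agonist

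*Protocol*

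**What the plan says.** **Entry rule (Protocol 3.1, criterion 3a).** The criterion reads, in part: "Premenopausal or perimenopausal women must receive concurrent treatment with a luteinizing hormone-releasing hormone (LHRH) agonist beginning at least 4 weeks before the start". The start meant is that of study treatment, and the agonist has to be kept up for as long as study drug is taken. The same criterion requires that they "agree to follow guidelines for use of highly effective contraception as outlined in Appendix C during the study"; this duty lasts until 90 days after the last dose. The agonist requirement recurs in Schedule of Assessments footnote h and in Section 7.2.

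**Contraception (Protocol Appendix C).** Acceptable methods are true abstinence, sterilization, a sterilized male partner, or a pair made of one item from list (a) and one barrier method from list (b). List (a) contains intrauterine devices and systems and "established use of oral, injected or implanted hormonal methods of contraception".

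**Drug restrictions.** Exclusion 1 in Section 3.2 bars "any cytotoxic chemotherapy, investigational agents or other anti-cancer drugs for the treatment of locally advanced or metastatic breast cancer within 14 days prior"; the window is counted back from first dose. Section 5.4.2 states: "No anticancer agents other than the study treatments should be given to patients". It adds that a patient who needs such an agent must be withdrawn first. Section 5.4.1 does not list LHRH agonists as permitted, but its list is expressly not exhaustive.

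**Analysis (SAP).** Section 5 analyses efficacy in the efficacy evaluable set as a whole and by ESR1 status; Section 3.4.5 gives summaries by dose level and overall. The baseline items named in Section 4.2 include neither menopausal status nor LHRH-agonist use. Section 6.9 says that "post-menopausal status will be listed only". Section 4.4 tabulates concomitant medications by drug class and preferred name, and lists them all.

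**The concern.** AC699 degrades ERα. The protocol's own background (Section 1.1) describes the oncogenic role of estrogen acting through its receptor, and 3a requires ovarian suppression in women who still have ovarian function. A contraception appendix that lets the same women take sex hormones works against that requirement. It matters to the statistician because such exposure is relevant to the drug's target in a trial whose dose levels have no control arm. The endpoints concerned are ORR, CBR, DCR, DOR and PFS (secondary) and the change in ERα expression in paired biopsies (exploratory). If the exposure occurs and is not marked beside the results, a reader of those outputs cannot take it into account.

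The second issue is operational. Sites must decide whether the agonist that 3a demands is an anticancer drug under exclusion 1 and Section 5.4.2. One answer leaves the woman on study; the other excludes or withdraws her. Sites that answer differently would produce inconsistent eligibility, deviation and withdrawal records.

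**Working it through.** There is no planned figure to reproduce. The check is a comparison of texts.

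| Rule | LHRH agonist | Exogenous sex hormones |
|---|---|---|
| Inclusion 3a, footnote h, Section 7.2 | Required | Not mentioned; contraception per Appendix C |
| Exclusion 1 | Not named, not excepted | Not named |
| Section 5.4.1 | Not listed; list is open | Not listed; list is open |
| Section 5.4.2 | Not named, not excepted | Not named |
| Appendix C | Not mentioned | Accepted with a barrier method |

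**Step 1: does the hormonal option apply to enrolled women?** Inclusion 3a refers them to Appendix C. The appendix opens with women of childbearing potential, gives fertile men their own condom-plus-spermicide rule, and addresses its list of unacceptable methods to women of childbearing potential. Nothing confines list (a) to partners of male patients. By its terms it applies to enrolled women.

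**Step 2: does another rule stop it?** The prohibitions in Section 5.4.2 concern investigational and anticancer therapy, coumarin anticoagulants, proton pump inhibitors and QT-prolonging drugs. Sex hormones are not among them. Section 5.4 tells patients to consult the study team before taking additional medications, but Appendix C speaks of established use, and a method already in use is not clearly additional. So the hormonal option stays open.

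**Step 3: would the agonist fall under the drug restrictions?** On timing, yes. It starts no later than 4 × 7 = 28 days before first dose and continues without a planned break, so it spans the whole 14-day window of exclusion 1 and the on-study period governed by Section 5.4.2. On classification, the documents do not say. Section 1.1 calls modulation of estrogen activity or synthesis the mainstay of treatment for ER-positive disease, so treating the agonist as an anticancer drug is a reasonable reading, but no passage classes it that way. Two outcomes follow:

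- If it is not an anticancer drug, 3a stands and nothing conflicts.
- If it is, exclusion 1 bars entry and Section 5.4.2 calls for withdrawal of a woman who did what 3a asked.

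The open list in Section 5.4.1 does not settle this, because that section makes other medications subject to Section 5.4.2.

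**Step 4: would the analysis show it?** In part. The Section 4.4 table and listing would show that LHRH agonists or hormonal contraceptives were used. They would not place that use beside a patient's response or ERα result, and the baseline tables would not show how many women entered under 3a at each dose level. The SAP still carries about 60 patients and 15 per expanded level, against about 100 and 20 in the protocol. It therefore appears to predate Version 4.0, which added 3a; that probably explains the gap.

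**The case against.** The best defence is that a specific mandate governs a general ban. The agonist requirement appears in 3a, footnote h and Section 7.2, while exclusion 1 and Section 5.4.2 never name LHRH agonists, and the permitted list is open-ended. This stands. A reader might infer that the protocol forbids the very drug it requires and that every woman entered under 3a is a deviation. The documents do not support that, since it depends on a classification they never make. What survives is a missing exception, with withdrawal as the consequence of one reading.

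On Appendix C, the defence is that hormonal methods are one option among several, that the list also serves partners of male patients, that no rule bans sex hormones, and that patients must consult before taking additional medications. All of this is true. It makes the provision a permission in tension with 3a rather than a breach of a stated ban. It does not close the gap, because the list is not limited to partners and the consultation rule does not clearly reach established use.

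On the analysis, the defence is that medications are already tabulated and listed, the endpoints are secondary or exploratory, the biopsies are optional, and no hypothesis is tested. These points stand and limit the SAP remedy to description.

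**Conclusion.** The point holds as a failure to align the treatment rules, with a small reporting gap in the SAP. It deserves correction because a stated rule permits exposure that runs against the purpose of 3a, and because one reading of another rule removes compliant patients. It does not touch the definition of the primary safety objective.

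Its size cannot be given. The documents state neither the number of pre- or perimenopausal women nor any response rate by menopausal status. A reader might assume a share and convert it into a shift in ORR or CBR; at an expanded level of about 20, one patient is 1/20 = 5 percentage points. That holds for any single patient and is not evidence of bias.

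A reader might also infer that newly started suppression is being credited to AC699. The agonist must start 28 days or more before first dose and the baseline scan is at most 28 days before it, so suppression begins on or before the scan date. How many women would be recently suppressed is unknown. Nor do the documents show that the date of last progression before entry is collected, so an analysis built on it cannot be assumed feasible.

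The conclusion rests on two readings: that the reference in 3a makes list (a) of Appendix C available to enrolled women, and that estrogen exposure is relevant to an ER-directed drug, as the protocol's background says.

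**What to change.** **Protocol.** In one amendment, reconcile inclusion 3a, exclusion 1, Sections 5.4.1 and 5.4.2 and Appendix C so that the LHRH agonist has the same status in each, and exogenous sex hormones likewise. Split Appendix C into methods for female patients and methods for partners of male patients. Which methods and drugs are allowed is the sponsor's clinical decision.

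**SAP.** Add menopausal status and LHRH-agonist use to the baseline tables in Section 4.2, by dose level and overall. Using the coded concomitant medication data, flag any exogenous sex-hormone use in the efficacy listings (Section 5) and the ERα listings (Section 7.2).

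**Cost.** Amendment wording with the usual approvals, a few table rows and one derived flag. Menopausal status is reviewed at screening and concomitant medications at each visit, so no new procedure is needed. The counts may be small, so the additions are descriptive and no subgroup inference should be drawn from them.

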Appendix D: New York Heart Association Classification of Cardiac Disease

The following table presents the New York Heart Association classification of cardiac disease.

Class	Functional Capacity	Objective Assessment
I	Subjects with cardiac disease but without resulting limitations of physical activity. Ordinary physical activity does not cause undue fatigue, palpitation, dyspnea, or anginal pain.	No objective evidence of cardiovascular disease.
II	Subjects with cardiac disease resulting in slight limitation of physical activity. They are comfortable at rest. Ordinary physical activity results in fatigue, palpitation, dyspnea, or anginal pain.	Objective evidence of minimal cardiovascular disease.
Ш	Subjects with cardiac disease resulting in marked limitation of physical activity. They are comfortable at rest. Less than ordinary activity causes fatigue, palpitation, dyspnea, or anginal pain.	Objective evidence of moderately severe cardiovascular disease.
IV	Subjects with cardiac disease resulting in inability to carry on any physical activity without discomfort. Symptoms of heart failure or the anginal syndrome may be present even at rest. If any physical activity is undertaken, discomfort is increased.	Objective evidence of severe cardiovascular disease.

Source: The Criteria Committee of New York Heart Association. Nomenclature and Criteria for Diagnosis of Diseases of the Heart and Great Vessels. 9th Ed. Boston, MA: Little, Brown & Co; 1994:253-256.

Final Protocol: 07 May 2024 Version 4.0

Appendix E: Hy's Law

Reference: FDA Guidance for Industry (issued July 2009) "Drug-induced liver injury: Premarketing clinical evaluation"

Introduction

This Appendix describes the process to be followed in order to identify and appropriately report cases of Hy's Law (HL). It is not intended to be a comprehensive guide to the management of elevated liver biochemistries.

During the course of the study, the Investigator will remain vigilant for increases in liver biochemistry. The Investigator is responsible for determining whether a subject meets potential Hy's Law (PHL) criteria at any point during the study.

The Investigator participates, together with Accutar Biotechnology, Inc. clinical project representatives, in review and assessment of cases meeting PHL criteria to agree whether HL criteria are met. Hy's Law criteria are met if there is no alternative explanation for the elevations in liver biochemistry other than drug-induced liver injury (DILI) caused by the investigational medicinal product.

The Investigator is responsible for recording data pertaining to PHL/HL cases and for reporting AEs and SAEs according to the outcome of the review and assessment in line with standard safety reporting processes.

Definitions

Potential Hy's Law (PHL)

Aspartate aminotransferase (AST) or alanine aminotransferase (ALT) $\ge 3 \times$ upper limit of normal (ULN) together with total bilirubin (TBL) $\ge 2 \times$ ULN at any point during the study following the start of study medication irrespective of an increase in alkaline phosphatase (ALP).

Hy's Law (HL)

Aspartate aminotransferase or ALT \geq 3 × ULN together with TBL \geq 2 × ULN, where no other reason other than the investigational product can be found to explain the combination of increases, e.g., elevated ALP indicating cholestasis, viral hepatitis, another drug.

For PHL and HL the elevation in transaminases must precede or be coincident with (i.e., on the same day) the elevation in TBL, but there is no specified time frame within which the elevations in transaminases and TBL must occur.

Identification of potential Hy's Law cases

In order to identify cases of PHL it is important to perform a comprehensive review of laboratory data for any subject who meets any of the following identification criteria in isolation or in combination:

- AST $>3 \times ULN$
- ALT >3 × ULN
- TBL \geq 2 × ULN

Study Drug: AC699

CONFIDENTIAL

Sponsor/Development Innovations Study Numbers: AC699-001/BRE 401

When a subject meets any of the identification criteria, in isolation or in combination, the central laboratory, if applicable, will immediately send an alert to the Investigator.

Where the identification criteria are met in samples analyzed by a local laboratory, the Investigator will:

- Notify the Sponsor's representative
- Request a repeat of the test (new blood draw) by the local laboratory
- Complete the appropriate unscheduled laboratory electronic case report form (eCRF) module(s) and the original laboratory test eCRF

When the identification criteria are met from central or local laboratory results the Investigator will without delay determine whether the subject meets PHL criteria (see "Definitions") by reviewing laboratory reports from all previous visits (including both central and local laboratory results).

The Investigator will without delay review each new laboratory report and if the identification criteria are met will:

- Notify the Sponsor's representative
- Determine whether the subject meets PHL criteria (see "Definitions") by reviewing laboratory reports from all previous visits
- Promptly enter the laboratory data into the laboratory eCRF

Follow-up

Potential Hy's Law criteria not met

If the subject does not meet PHL criteria the Investigator will:

- Inform the Sponsor's representative that the subject has not met PHL criteria
- Perform follow-up on subsequent laboratory results according to the guidance provided in the clinical study protocol

Potential Hy's Law criteria met

If the subject does meet PHL criteria the Investigator will:

- Determine whether PHL criteria were met at any study visit prior to starting study treatment (see Section 11 Safety Reporting)
- Notify the Sponsor's representative that the subject has met PHL criteria

The Investigator contacts the Medical Monitor, to provide guidance, discuss, and agree an approach for the study subjects' follow-up and the continuous review of data. Subsequent to this contact the Investigator will:

- Monitor the subject until liver biochemistry parameters and appropriate clinical symptoms and signs return to normal or baseline levels, or as long as medically indicated
- Investigate the etiology of the event and perform diagnostic investigations as discussed with the Medical Monitor.
- Complete the liver eCRF modules as information becomes available
- If at any time (in consultation with the Medical Monitor) the PHL case meets serious criteria, report it as an SAE using standard reporting procedures.

CONFIDENTIAL

Sponsor/Development Innovations Study Numbers: AC699-001/BRE 401

Final Protocol: 07 May 2024 Version 4.0

Review and assessment of potential Hy's Law cases

The instructions in this section should be followed for all cases where PHL criteria are met.

No later than 3 weeks after the biochemistry abnormality was initially detected, the Investigator contacts the Medical Monitor in order to review available data and agree on whether there is an alternative explanation for meeting PHL criteria other than DILI caused by the investigational product. The Accutar Biotechnology, Inc. Clinical Lead or equivalent and Medical Monitor will also be involved in this review together with other subject-matter experts as appropriate.

According to the outcome of the review and assessment, the Investigator will follow the instructions below.

If there is an agreed alternative explanation for the ALT or AST and TBL elevations, a determination of whether the alternative explanation is an AE will be made and subsequently whether the AE meets the criteria for a SAE:

- If the alternative explanation is not an AE, record the alternative explanation on the appropriate eCRF.
- If the alternative explanation is an AE/SAE, record the AE/SAE in the eCRF accordingly and follow the reporting standard practices.

If it is agreed that there is no explanation that would explain the ALT or AST and TBL elevations other than the investigational product:

Report an SAE (report term Hy's Law) according to the Sponsor's standard processes.

- The 'Medically Important' serious criterion should be used if no other serious criteria apply.
- As there is no alternative explanation for the HL case, a causality assessment of 'related' should be assigned.

If there is an unavoidable delay of over 3 weeks in obtaining the information necessary to assess whether or not the case meets the criteria for HL, then it is assumed that there is no alternative explanation until such time as an informed decision can be made:

- Report an SAE (report term Potential Hy's Law) applying serious criteria and causality assessment as per above.
- Continue follow-up and review according to the agreed plan. Once the necessary
 supplementary information is obtained, repeat the review and assessment to determine
 whether HL criteria are met. Update the SAE report according to the outcome of the
 review amending the reported term if an alternative explanation for the liver biochemistry
 elevations is determined.

Actions required when potential Hy's Law criteria are met before and after starting study treatment

This section is applicable to subjects with liver metastases who meet PHL criteria on study treatment having previously met PHL criteria at a study visit prior to starting study treatment.

At the first on-study treatment occurrence of PHL criteria being met, the Investigator will determine if there has been a significant change in the subjects' condition compared with the last visit where PHL criteria were met.

CONFIDENTIAL

Sponsor/Development Innovations Study Numbers: AC699-001/BRE 401

Final Protocol: 07 May 2024 Version 4.0

- If there is no significant change, no action is required.
- If there is a significant change, notify the Sponsor's representative.

A "significant" change in the subject's condition refers to a clinically relevant change in any of the individual liver biochemistry parameters (ALT, AST, or TBL) in isolation or in combination, or a clinically relevant change in associated symptoms. The determination of whether there has been a significant change will be at the discretion of the Investigator, this may be in consultation with the Medical Monitor if there is any uncertainty.

Actions required for repeat episodes of potential Hy's Law

This section is applicable when a subject meets PHL criteria on study treatment, and has already met PHL criteria at a previous on-study treatment visit.

The requirement to conduct follow-up, review, and assessment of a repeat occurrence(s) of PHL is based on the nature of the alternative cause identified for the previous occurrence.

The Investigator should determine the cause for the previous occurrence of PHL criteria being met and answer the following question:

Was the alternative cause for the previous occurrence of PHL criteria being met found to be the disease under study (e.g., chronic or progressing malignant disease, severe infection, or liver disease), or did the subject meet PHL criteria prior to starting study treatment and at first onstudy treatment visit, as described in "Actions required when potential Hy's Law criteria are met before and after starting study treatment".

- If No: Follow the process described in "Potential Hy's Law criteria not met".
- If Yes: Determine if there has been a significant change in the subject's condition compared with when PHL criteria were previously met.

If there is no significant change, no action is required.

If there is a significant change, follow the process described in "Follow-up".

A "significant" change in the subject's condition refers to a clinically relevant change in any of the individual liver biochemistry parameters (ALT, AST, or TBL) in isolation or in combination, or a clinically relevant change in associated symptoms. The determination of whether there has been a significant change will be at the discretion of the Investigator; this may be in consultation with the Medical Monitor if there is any uncertainty.

CONFIDENTIAL

Sponsor/Development Innovations Study Numbers: AC699-001/BRE 401

Final Protocol: 07 May 2024 Version 4.0

